8.4. Derived and Computed Variables

The following derived and computed variables have been initially identified as important for the analysis of the primary and secondary target variables. It is expected that additional variables will be required. The SAP will not be amended for additional variables that are not related to the primary target or key secondary target variables. Any additional derived or computed variables will be identified and documented in the SAS programs that create the analysis files. If the SAP is not amended, further derivations related to primary and secondary target variables will be described in the CSR.

- **Age** will be derived according to the usual definition that a person is n years old until she or he has completed her or his (n+1)th year of life, using the date of informed consent as the reference date. This is also the definition that will be applied for evaluation of the age related inclusion criteria, and the definition of the age groups used for analysis. [Unit: years]
- **Body Mass Index**: BMI = (Body weight) / Height² [Unit: kg/m²]

9. Study Subjects and Demographics

9.1. Disposition of Subjects and Withdrawals

All patients enrolled in the study will be accounted for. Descriptive summaries of population data will be provided overall and by age group; these will include:

- The frequency and percent of patients in each analysis population and age group.
- The disposition of patients (including number of patients enrolled, number of patients treated, number of completers)
- Study withdrawals by reason of withdrawal

9.2. Protocol Deviations

Protocol deviations will be checked on complete data for all patients prior to defining the analysis populations. The final decision regarding inclusion/exclusion of patients from the analysis sets will be taken based on protocol adherence reports during data review meetings before database lock, data release and analysis, applying the definitions in section 7.

Major protocol deviations will be summarized by type of deviation and by age group. Individual patients with these protocol deviations will be listed.

9.3. Demographics and Other Baseline Characteristics

Descriptive summaries of the demographic and other baseline characteristics will be completed for the populations specified below, overall and by age group; these include:

 Demographics (Age, Gender, Race/Ethnicity, Height, Weight, BMI (calculated), ABO blood group)

(SAF, FAS, PP)

Medical History (SAF)

Medical history will be coded with the Medical Dictionary for Regulatory Activities (MedDRA, according to the version specified in the Data Management Plan). Incidences of findings in medical history will be summarized by MedDRA system organ class (SOC) and preferred term (PT)

Prior and Concomitant Medications (SAF)

Medications will be coded using the WHO Drug Dictionary (according to the version specified in the Data Management Plan). Incidences of prior and concomitant medications will be summarized by ATC level 2 and ATC level 4

Baseline Physical Examination, including vital signs (SAF)

9.4. Measurement of Treatment Compliance

The following parameters will be listed and/or summarized per patient and/or per infusion:

- Body weight
- Total volume (mL) of octaplas (blood group specific / blood group compatible) and FFP (if applicable) used per infusion episode and in total

- Actual dose (mL/kg) per infusion episode and in total (based on the latest available weight measurement for each TPE)
- Total number of infusions administered
- Total number of bags administered
- Infusion times and rates
- Overall amount of product administered and batches used (only included in data listings)

10. Efficacy Analysis

Efficacy will not be assessed.

16/21

11. Safety and Tolerability Analyses

To primary objective of LAS-213 is to assess safety and tolerability of octaplas in the pediatric population by monitoring SAEs, ADRs, TEs, TEEs, and by measuring safety laboratory parameters. This will be done by means of descriptive analyses of all safety related data available for the Safety Population.

11.1. SAEs, ADRs, TEs, and TEEs

A Serious Adverse Event (SAE) is any untoward medical occurrence at any dose that

- results in death
- is life-threatening
- requires in-patient hospitalization or prolongation of existing hospitalization
- results in persistent or significant disability/incapacity
- is a congenital anomaly/birth defect
- is another important medical event

An Adverse Drug Reaction (ADR) in the context of this study is any noxious and unintended response to octaplas related to any dose; this means that a causal relationship between octaplas and the reported reaction cannot be ruled out, i.e. the relationship must be determined to be at least possibly related to administration of *octaplas* by the investigator or by Octapharma's medical expert or an adjudicator of the independent data monitoring committee (TEEs and TEs). Reactions with a missing or indeterminate causality assessment will also be classified as ADRs.

Serious Adverse Events (SAEs), Thrombotic events (TEs) and thromboembolic events (TEEs) will be handled in exactly the same fashion as ADRs in the context of the safety analysis. The only difference is that TEs and TEEs will be included in the analysis regardless of the causality assessment; even if such an event is reported as not related to study drug, it will be included in all data listings and tabulations. For the remainder of this section the term 'event' will thus be used to refer to any ADR, TE, or TEE.

All of the below will feature this classification (SAE, ADR, TE, TEE) as additional event characteristic if applicable.

All events for each patient, including multiple occurrences of the same reaction, will be listed in full detail, including reported term, MedDRA preferred term and system organ class, onset, duration, time to the event occurrence from last dose, causality, dosage, severity, seriousness and actions taken. The listing will include the number of the last infusion prior to each event and the relative time. An evaluation to identify any event with increased frequency over time will be performed.

For each age group and for the study as a whole the following will be given:

- Total number of events reported
- Number of events divided by the total number of TPEs

On a per patient basis the incidence of events will be summarized by system organ class, preferred term and maximum severity. If a patient experiences an event more than once the event at the most severe occurrence will be considered. Patients will be included only once

under each system organ class and only once in the overall totals under the most severe occurrence.

Events will be summarized by strongest relationship to study medication, by system organ class and preferred term. If a patient experiences an event more than once the event most related to study medication will be considered. Patients will be included only once under each system organ class and only once in the overall totals under the most related to study medication occurrence.

Incidences of events (given as the number and percentage of patients) will be summarized overall and for each age group as follows:

- Events by system organ class, preferred term and maximum severity
- Events by system organ class, preferred term and strongest relationship
- Serious events by system organ class and preferred term
- Non-serious events by system organ class and preferred term
- Events leading to withdrawal by system organ class and preferred term
- Events leading to death by system organ class and preferred term
- Other significant events by system organ class and preferred term*

Narratives will be prepared describing each death, each other serious event and those of the other significant events that are judged to be of special interest because of clinical importance. The narrative will address the following: nature and severity of reaction, clinical course leading up to event, indication of timing relevant to investigational medicinal product administration, relevant laboratory measurements, whether the drug was stopped, countermeasures or postmortem findings, if any, and a causality assessment.

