5.2. Final Analyses and Reporting

The purpose of this study is to assess safety and tolerability of octaplas™ in the pediatric population by monitoring SAEs, ADRs, TEs, TEEs, and by measuring safety laboratory parameters. No confirmatory testing is planned, but all data collected will be explored and presented descriptively in full detail, by age group as well as in total, to facilitate the review of population homogeneity and general patterns within and between the age groups. Any p-value or confidence interval presented is to be understood in the exploratory sense.

To facilitate the detection of any possible safety signal, all SAEs, ADRs, TEs, and TEEs will be characterized and analyzed by seriousness, severity, relation to study drug and timely relationship to study drug administration. In addition to these pre-planned categories the collected data will be examined to identify additional characteristics of interest such as particular indications for TPE, relevant concomitant medications, or SMQs covering a noticeable number of events. The rates of SAEs, ADRs, TEs, and TEEs will be presented for all these categories, together with the associated 95% confidence intervals, again per age group and in total.

Individual patient profiles or tabulations will be generated, displaying the baseline characteristics as well as all interventions, treatment details and measurements on a time scale. This will facilitate the review of each individual course of treatment by a medical expert to detect any safety signal that might not be reflected in the event rates.

6. Sample Size Determination

A minimum of forty (40) pediatric patients aged \geq 2 years to \leq 20 are planned to be enrolled into this study. The chosen number of 40 pediatric patients is not derived from statistical considerations of power, but to gather enough clinical evidence to obtain a sound and meaningful medical assessment.

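### SAP 11.1 leaves SAEs out of its definition of an event, so its tables as written drop SAEs that are unrelated and non-thrombotic, against SAP 5.2 and Protocol 9.2 and 9.2.3

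*SAP*

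**What the plan says.** SAP 11.1 begins by defining an SAE by the usual seriousness criteria, with no causality condition. It then defines an ADR as a reaction judged at least possibly related by the investigator, by the sponsor's medical expert or, for TEs and TEEs, by an adjudicator of the monitoring committee. It adds: "Reactions with a missing or indeterminate causality assessment will also be classified as ADRs".

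Next it states that SAEs, TEs and TEEs are treated identically to ADRs, with one exception: "The only difference is that TEs and TEEs will be included in the analysis regardless of the causality assessment". It concludes: "For the remainder of this section the term 'event' will thus be used to refer to any ADR, TE, or TEE". The sentence after that reads: "All of the below will feature this classification (SAE, ADR, TE, TEE) as additional event characteristic if applicable".

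The rest of 11.1 uses the defined term throughout: the full listing, the total count, the count divided by the number of plasma exchanges, and seven incidence tables. Among these are serious events, events leading to withdrawal, and "Events leading to death by system organ class and preferred term". Narratives are specified separately: "Narratives will be prepared describing each death, each other serious event".

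SAP 5.2 is broader. There, "all SAEs, ADRs, TEs, and TEEs will be characterized and analyzed by seriousness, severity, relation to study drug", and "The rates of SAEs, ADRs, TEs, and TEEs will be presented for all these categories, together with the associated 95% confidence intervals". Protocol 9.2 includes the occurrence of all SAEs in the safety assessment. Protocol 9.2.3 has SAEs reported and analysed by relation to study drug.

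**The concern.** If SAEs follow the ADR rules and only TEs and TEEs are excused from the causality condition, an SAE must be possibly related or thrombotic to count as an event. A table headed as serious events would then hold only related or thrombotic serious events, and its figures would not match the SAE rates that SAP 5.2 promises.

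This matters more here than in most trials. Protocol 7.3.1 keeps non-serious adverse events out of the case report form unless they are TEs or TEEs, so SAEs are the only non-thrombotic adverse events collected whatever their cause. The study has no control group. A reader who doubts the assessors' causality calls needs the all-causality SAE counts to check them, and the 11.1 tables would not supply them.

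**Working it through.** The plan gives no figure on this point to reproduce. The sample size, a minimum of 40, is expressly not based on power (Protocol 9.1, SAP 6). The check therefore compares two sets of events and then illustrates the size of the difference.

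**Step 1: the two sets.** Classify each adverse event as serious or not, related or not (related includes missing or indeterminate causality), and thrombotic (TE or TEE) or not.

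- SAP 11.1 event, read literally: related OR thrombotic.
- Set promised by SAP 5.2 and Protocol 9.2: serious OR related OR thrombotic.

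| Serious | Related | Thrombotic | SAP 11.1 | SAP 5.2 / Protocol 9.2 |
|---|---|---|---|---|
| no | no | no | out | out |
| no | no | yes | in | in |
| no | yes | no | in | in |
| no | yes | yes | in | in |
| **yes** | **no** | **no** | **out** | **in** |
| yes | no | yes | in | in |
| yes | yes | no | in | in |
| yes | yes | yes | in | in |

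Exactly one of the 8 combinations differs: serious, not related, not thrombotic. Such cases are foreseen. Protocol 7.3.2.4 lets an adverse event be rated unlikely or not related, Protocol 7.3.3 has all SAEs reported after the first administration, and Protocol 7.3.4 sends not-related SAEs to quarterly committee review. The data would therefore exist.

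**Step 2: illustrative size.** Input from the documents: n = 40. Inputs assumed, because no SAE rate is given: 5%, 10% or 20% of patients have only an unrelated, non-thrombotic SAE. Patients missing from the table: 40 × 0.05 = 2; 40 × 0.10 = 4; 40 × 0.20 = 8.

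Exact (Clopper-Pearson) 95% limits for k of n patients are the 2.5% quantile of Beta(k, n − k + 1) and the 97.5% quantile of Beta(k + 1, n − k). For k = 0 the lower limit is 0 and the upper limit is 1 − 0.025^(1/40) = 8.8%.

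| Patients omitted (assumed) | Patients with a related SAE (assumed) | Literal 11.1 table | All-causality table |
|---|---|---|---|
| 2 | 0 | 0/40: 0% (0–8.8%) | 2/40: 5.0% (0.6–16.9%) |
| 4 | 0 | 0/40: 0% (0–8.8%) | 4/40: 10.0% (2.8–23.7%) |
| 8 | 0 | 0/40: 0% (0–8.8%) | 8/40: 20.0% (9.1–35.6%) |
| 2 | 1 | 1/40: 2.5% (0.1–13.2%) | 3/40: 7.5% (1.6–20.4%) |
| 4 | 1 | 1/40: 2.5% (0.1–13.2%) | 5/40: 12.5% (4.2–26.8%) |
| 8 | 1 | 1/40: 2.5% (0.1–13.2%) | 9/40: 22.5% (10.8–38.5%) |

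**Step 3: the repaired definition.** With an event defined as any SAE, ADR, TE or TEE, and SAEs admitted regardless of causality, the two sets agree in all 8 combinations.

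**The case against.** The strongest reply is that most of the SAP points away from the literal reading. The heading of 11.1 names SAEs, the section opens by defining them without a causality condition, and the classification line lists SAE as a class of its own. The opening of section 11 promises all available safety data. On that evidence the omission is a drafting slip that a careful programmer would catch. This stands as to intent. It does not settle the specification: the classification line labels items already admitted, where applicable, and a serious ADR can also carry the SAE label.

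A second reply is that the primary endpoint concerns events caused by the product (SAP 3.2.1), so a related-only SAE count is defensible. That wording cannot explain the gap, because unrelated TEs and TEEs fall under the same endpoint and are included. Nor does it remove the promise of all SAEs in SAP 5.2 and Protocol 9.2.

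Third, Protocol 7.3.2.2 could be read as collecting adverse events more widely, which would make SAEs less singular. Protocol 7.3.1 is the express rule, however, and it excludes non-serious events other than TEs and TEEs. The contradiction over SAEs does not depend on this.

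Three limits do stand. The separate table list is still to come and could resolve the point. Each death gets a narrative whatever its cause, although whether non-fatal unrelated SAEs do depends on the same defined term. The SAE rates used above are assumptions.

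**Conclusion.** The concern holds as a contradiction within the plan. SAP 11.1 as written excludes one class, SAEs that are neither related nor thrombotic, from every output built on its defined term. SAP 5.2 and Protocol 9.2 include that class, and Protocol 9.2.3 presupposes it by analysing SAEs by relation to study drug. It is not an established loss from every safety output: TE and TEE counts, laboratory and vital-sign listings, committee review and death narratives are unaffected, and the SAE rates in SAP 5.2 remain promised.

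The practical size cannot be known from the documents. Under the assumed 5% to 20% of 40 patients, 2 to 8 patients would be missing from the serious-event table. It should be corrected, because it touches a component of the primary endpoint and the plan currently specifies two different tables. Confidence is high on the wording mismatch; the effect on the results depends on how 11.1 is programmed and on how many such SAEs occur.

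**What to change.** Before database lock:

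1. In SAP 11.1, define an event as any SAE (regardless of causality), ADR, TE or TEE.
2. Reword the waiver sentence so that SAEs, TEs and TEEs are all included whatever the causality assessment.
3. Show related SAEs as a separate sub-row, so that a count matching the causal wording of the primary endpoint stays visible.
4. Carry the same definition into the separate list of tables, listings and figures.

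As a secondary point of wording, Protocol 2, 3.1.1 and 3.3.2 omit SAEs and should be aligned with the synopsis.

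The cost is two SAP sentences and one sub-row; the data are already collected. The new definition does flow through the listing, the totals, the events per plasma exchange and all seven incidence tables, so any unrelated SAEs will raise the overall counts and make the serious-event rate less favourable. The event classification already planned in 11.1, together with the sub-row, keeps the related counts separable.

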5.4 Dose and Dosing Schedule

octaplasTM, ABO blood group specific, will be given as replacement fluid during TPE and administered per institutional standard of care. It will be used in lieu of FFP during the treatment period.

The total octaplasTM volume infused and time details of each infusion episode will be recorded.

Patients will be followed for one week (7 days) during their therapy which could consist of one or more TPE procedures. The recommended dose is a total plasma volume between 40 to 60 mL/kg, as prescribed by the treating physician. The dosing regimen might differ from the general recommendation, depending on the therapeutic treatment plan and the investigator's evaluation of the respective clinical situation (e.g. plasma exchange). The infusion rate of octaplasTM should not exceed 0.020-0.025 mmol/kg BW (body weight)/min, which is equal to <1 mL/kg BW/min.

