5.5 Preparation and Method of Administration

octaplasTM will be used per the approved labeling for the product (see **Appendix 1**). octaplasTM will be administered based on ABO-blood group specificity. In urgent cases, or in circumstances that no same blood group is available (type A octaplasTM for type A recipient), the patient can be administered octaplasTM that is compatible to the recipient's blood group (e.g. type AB octaplasTM can be administered to a type A recipient).

All attempts should be made to ensure adequate octaplasTM blood-type specific inventory is available to meet patient orders. Shipment requests to Octapharma should coincide to meet these needs and should be issued promptly, taking into consideration processing and shipment time.

During the study treatment period, the hierarchy of plasma choice is:

- 1. octaplas™ blood group specific
- 2. octaplasTM blood group compatible
- 3. FFP

Further, if plasma is needed during the TPE follow-up period, octaplasTM should be administered.

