3.2. Study Endpoints (Target Variables)

3.2.1. Primary Endpoint

The primary endpoint is the monitoring of SAEs, ADRs, TEs and TEEs caused by the octaplas™ used for therapeutic plasma exchange (TPE). All such events will be listed and the rate of such reactions per patient and per TPE procedure will be calculated, overall as well as for all relevant combinations of age groups and reaction characteristics.

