Categorical, qualitative variable summaries will include the frequency and percentage of patients who are in the particular category. In general the denominator for the percentage calculation will be the total number of patients in the analysis population unless otherwise specified.

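### Does counting all TPEs in the per-TPE rate, with no clustered interval named, distort a primary result?

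*SAP*

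**What the plan says.** SAP section 3.2.1 gives the primary endpoint two forms: "the rate of such reactions per patient and per TPE procedure will be calculated". SAP section 11.1 carries out the second as "Number of events divided by the total number of TPEs", for each age group and for the whole study. In that section an event is an ADR, a TE or a TEE. TEs and TEEs count whatever their causality, and a reaction whose causality is missing or indeterminate counts as an ADR.

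On which plasma is used, Protocol section 5.4 says of octaplas: "It will be used in lieu of FFP during the treatment period". Protocol section 5.5 then sets out a ranking ("During the study treatment period, the hierarchy of plasma choice is") with blood-group-specific octaplas first, compatible octaplas second and FFP third. It adds that octaplas should be given "if plasma is needed during the TPE follow-up period". The safety population in SAP section 7 selects patients with at least one octaplas infusion; it does not select procedures.

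On intervals, SAP section 5.2 says that rates by event category will be shown "together with the associated 95% confidence intervals, again per age group and in total", and also that "Any p-value or confidence interval presented is to be understood in the exploratory sense". No interval method is named. SAP section 8 says that, in general, "the denominator for the percentage calculation will be the total number of patients in the analysis population".

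**The concern.** There are two apparent faults.

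**Denominator.** The endpoint is about octaplas, yet the divisor counts every exchange. An exchange done with FFP alone is not an octaplas exposure, but it would still enlarge the divisor and could make octaplas look safer than it is. A smaller mismatch runs the other way: octaplas given as plasma in follow-up can add an ADR with no matching TPE.

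**Interval.** A child may have several TPEs in the week, and repeat occurrences of the same reaction are counted. If the 95% intervals extend to the per-TPE rate and an analyst pools all procedures in one Poisson or binomial interval, that interval ignores differences between children and can be too narrow.

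At stake is how one of the two forms of the primary endpoint is read, in a required pediatric safety study.

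**Working it through.** **Inputs.** The documents give a minimum of 40 patients, with no power basis (SAP section 6), and one or more TPEs per child in 7 days (SAP section 4.1). They give no FFP-only share, event rate, mean number of TPEs per child or degree of clustering, so there is no figure in the plan to reproduce. Everything below is an assumed illustration.

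**Step 1: denominator.** Let E be counted events, T all TPEs, F the FFP-only TPEs, and e the counted events that follow those F procedures.

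- Rate as planned: E/T.
- Rate matched to octaplas procedures: (E − e)/(T − F).
- Ratio of planned to matched: (1 − F/T)/(1 − e/E).

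Take T = 120 (40 children × 3) and E = 24, so the planned rate is 24/120 = 0.200.

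| F | e | Matched rate | Planned ÷ matched |
|---|---|---|---|
| 0 | 0 | 24/120 = 0.200 | 1.000 |
| 1 | 0 | 24/119 = 0.202 | 0.992 |
| 6 | 0 | 24/114 = 0.211 | 0.950 |
| 12 | 0 | 24/108 = 0.222 | 0.900 |
| 6 | 1 | 23/114 = 0.202 | 0.991 |
| 6 | 2 | 22/114 = 0.193 | 1.036 |

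The 0.8%, 5% and 10% understatements all need e = 0. SAP section 11.1 does not guarantee that. TEs and TEEs count regardless of cause. A reaction after an FFP-only exchange, in a child given octaplas earlier that week, is an ADR if a link cannot be ruled out or the causality is missing. With F = 6 the planned rate is exact at e = 24 × 6/120 = 1.2 events and too high above that.

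The obvious repair drops FFP-only TPEs from the divisor but keeps every event, giving 24/114 = 0.211. With e = 1 that is 24/23 = 1.043 times the matched rate; with e = 2, 24/22 = 1.091 times. Removing those events instead would conflict with the rule that all TEs and TEEs are tabulated, and could discard late effects of earlier octaplas.

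The follow-up mismatch is of similar size: 1 of 24 ADRs arising outside a TPE raises the rate by 24/23 − 1 = 4.3%.

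**Step 2: is a per-TPE interval planned?** SAP section 5.2 attaches intervals to rates by category. The category tables in SAP section 11.1 are numbers and percentages of patients, and SAP section 8 makes patients the default denominator for percentages. On that reading each child counts once and clustering does not arise. SAP section 3.2.1, which uses the word rate for both forms, supports the other reading. The text settles neither.

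**Step 3: size if one is produced.** For m TPEs per child, rate r and between-child gamma variance v, the variance of the count is inflated by 1 + r·m·v:

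- r = 0.05, m = 3, v = 1: 1 + 0.15 = 1.15, so a width factor of √1.15 = 1.07.
- r = 0.2, m = 5, v = 2: 1 + 2 = 3, so √3 = 1.73.

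Simulated coverage of a pooled exact Poisson 95% interval with 40 children, for v = 0 / 0.5 / 1 / 2:

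| Events per TPE | 1–5 TPEs per child | 3–7 TPEs per child |
|---|---|---|
| 0.2 | 96/92/88/81% | 96/90/85/75% |
| 0.1 | 97/95/93/89% | 96/93/91/85% |
| 0.05 | 97/96/95/94% | 97/96/94/91% |
| 0.02 | 98–99% | 95–97% |

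A log-scale interval clustered by child covers 94–97% throughout, at 0.98 to 1.70 times the Poisson width. In an assumed age group of 10 at 0.05 events per TPE, the pooled interval already covers 96–99%, and the clustered one is 1.23 to 1.51 times as wide. At high rates with strong clustering, small groups show a shortfall too.

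**Step 4: what the reader will see anyway.** SAP section 9.4 covers octaplas and FFP volume per infusion episode, and infusion times. SAP section 11.1 lists every event with the last infusion number, time from last dose and causality. SAP section 5.2 adds patient profiles of all interventions on a time scale. FFP-only TPEs, and events after them, can be found from these.

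**The case for a change.** The strongest case for a change is that the per-TPE rate is one of two stated forms of the primary endpoint, in a study requested by the regulator. Calling intervals exploratory removes a decision rule, but it does not excuse a rate that fails to mean what it says. The sponsor foresaw FFP, planned to record it and did not carry it into the rate. Two analysts could give different intervals from the same data. One or two sentences would settle both matters with data already planned, and if FFP is never used the wording costs nothing.

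Much of this stands. The text is read correctly, no interval method is named, and a pooled interval would be plainly too narrow if events were frequent and strongly clustered.

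Three parts do not stand. The claim that the planned rate is biased downward depends on FFP-only TPEs yielding no counted event. The restricted divisor brings a mismatch of its own, so it is an alternative and not a correction. And the plan commits to no pooled interval: the fault would lie in an analyst's choice that the SAP does not make.

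**Conclusion.** No change to the plan is needed. SAP section 11.1 does what SAP section 3.2.1 says: it gives a rate per TPE procedure, with events and procedures counted over the same treatment week. Octaplas is the default plasma and zero FFP-only TPEs is plausible. If some occur, the illustrated effect is 0.8% to 10% downward when they yield no counted event, and 3.6% upward with two such events after six FFP-only TPEs.

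The missing interval method is a gap that a competent analyst fills at programming: exact intervals for patient incidence and, if an overall per-TPE interval is shown, some allowance for repeats within a child. Prescribing a large-sample clustered interval everywhere would widen the intervals in small age groups at low event rates with no coverage to recover.

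This rests on assumed event rates, TPE counts, FFP shares and clustering, none of which the documents give. It also rests on the study's being descriptive, with no test, power basis or decision rule. Frequent FFP-only TPEs, or about 0.2 events per TPE with strong clustering, would call for care in reading the rate, and the planned listings would show either.
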